### 6.3.3 Other possible concomitant therapies

Analgesic treatment, transfusion of blood products, electrolyte and glucose infusions, i.v. parenteral nutrition, inotropic support, antibiotics, anti-fungal and anti-viral treatment, ultrafiltration or hemodialysis, as well as general supportive care (e.g. gastro-protective agents, anti-hypertensive etc.) are permitted during the study.

The use of any prescription or over-the-counter medication, including herbal and homeopathic preparations with the exception of multi-vitamins, needs to be notified to the Investigator.

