### 6.3.4 Not allowed concomitant therapies

Tocilizumab, canakinumab or TNF inhibitors have to be discontinued before initiation of emapalumab treatment.

As long as emapalumab is being administered, no concomitant use of etoposide, T-cell depleting agents, or any other biologic drug is allowed with the exception of:

- ✓ G-CSF, in case of prolonged neutropenia
- ✓ Rituximab, in case of documented EBV infection
- ✓ Anakinra, if administered as described in [section 6.3.1](#)

Vaccination with a live or attenuated-live (including BCG) vaccine must be avoided during the whole study. In the event that emapalumab concentrations are still measurable after the end of the study, the period with no vaccinations should be extended until serum emapalumab levels are no longer detectable.

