## 7.4 EFFICACY ENDPOINTS

The efficacy of emapalumab in this patient population will be evaluated based on the evolution of the MAS distinct features of cytopenias, liver function and coagulopathy.

In particular the following variables will be assessed:

- Number of patients achieving MAS remission by Week 8 after initiation of emapalumab treatment.
- Time to MAS remission.
- Number of patients for whom at any time during the study glucocorticoids can be tapered *i)* to the same (or lower) dose being administered before the occurrence of MAS (in those patients who are already treated for sJIA/AOSD) or *ii)* by 50% (or less) of the dose administered at emapalumab treatment start (in those patients who present with MAS at sJIA/AOSD onset).
- Time to achievement of glucocorticoids tapering (as defined above).
- Survival time.
- Number of patients withdrawn from the study due to lack of efficacy.

MAS remission is defined as

- ✓ Resolution of clinical signs and symptoms according to the Investigator and
- ✓ Normalization of laboratory parameters relevant to MAS, as follows:
  - WBC and platelet count above LLN
  - LDH below 1.5 ULN
  - ALT/AST below 1.5 ULN
  - fibrinogen higher than 100 mg/dL
  - ferritin levels decreased by at least 80% from values at screening or baseline (whichever is higher) or below 2000 ng/ml, whichever is lower.

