• by at least 50% of the equivalent dose of prednisone administered at emapalumab treatment start (in those patients who present with MAS at sJIA/AOSD onset).

The daily equivalent dose of prednisone will be compared with the daily equivalent dose of prednisone at SD0.

AD-ST-33.04 Effective date: 30-Jun-2017

Version 2.0 | Date 29-Oct-2020 | AD-PR-109.01 Effective date: 26-Jun-2017

Page 23 of 51

If it is not possible to establish if a patient has been treated for sJIA/AOSD or not before study start for all patients, or if it is not possible to retrieve glucocorticoids dose administered before the occurrence of MAS for all patients who already are treated for sJIA/AOSD, the glucocorticoids tapering endpoint will be changed. In this case the endpoint will be: "glucocorticoids permanently tapered at any time during the study by at least 50% of the equivalent dose of prednisone administered at emapalumab treatment start (SD0).

If glucocorticoid dosing data are unavailable at a given time point, the assumption that dose has not been further tapered from the previous available observation will be made. Glucocorticoid doses will be calculated as (prednisone-equivalent) mg/kg/day.

- MAS remission = resolution of clinical signs and symptoms according to the Investigator (MAS clinical signs and symptoms score ≤ 1) AND normalization of laboratory parameter relevant to MAS as follows:
  - White blood cell count (WBC) and platelet count above the lower limit of normal (LLN)
  - Lactate dehydrogenase (LDH) below 1.5 upper limit of normal (ULN)
  - Alanine aminotransferase/aspartate aminotransferase (ALT/AST) below 1.5 ULN
  - Fibrogen higher than 100 mg/dL
  - Ferritin level decreased by at least 80% from values at screening or baseline (whichever is higher) or below 2000 ng/mL, whichever is lower

If one or more laboratory data are unavailable within the visit window, the LOCF approach will be used.

- MAS remission by week 8 = patients who meet MAS remission conditions in the period SD56  $\pm$  5 days regardless the time of first MAS remission or its duration.
- Survival:

Time to death = date of death - date of first emapalumab infusion + 1

Patients who survive to the end of the study will be censored at the date of last contact. In case in which a patient withdrew consent the censoring date will be the date of withdrawal of consent.

• Time to MAS remission:

AD-ST-33.04 Effective date: 30-Jun-2017

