## 9.5.4. Other Exploratory Analyses

Other exploratory analyses of safety data, including summaries for different subsets of patients, may be conducted. Any unplanned exploratory analysis performed will be clearly identified as such in the final CSR.

Data in the following CRF forms will be included in listings only:

- Imaging
- Brain magnetic resonance imaging (MRI)
- Cerebrospinal fluid (CSF) analysis
- Hospitalization
- Concomitant procedures
- Transfusion

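### MAS remission scores platelets, WBC and fibrinogen without regard to recent blood products or G-CSF, and no sensitivity analysis tests whether this matters

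*SAP*

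**What the plan says.** SAP 6.1.7 defines MAS remission as a conjunction. The Investigator's signs-and-symptoms score must be 1 or less, and every laboratory criterion must hold: "White blood cell count (WBC) and platelet count above the lower limit of normal (LLN", LDH and ALT/AST below 1.5 times ULN, "Fibrogen higher than 100 mg/dL" (the SAP's spelling of fibrinogen) and a ferritin criterion. Protocol 7.4 uses the same thresholds, for example "WBC and platelet count above LLN". Neither text asks whether the patient had recently received a product that raises the value.

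Such products are allowed. Protocol 6.3.3 lists "transfusion of blood products" among the permitted therapies. Protocol 6.3.4 names "G-CSF, in case of prolonged neutropenia" as an exception to the restriction on other biologics that applies while emapalumab is being given.

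On the use of these data, SAP 9.5.4 states: "Data in the following CRF forms will be included in listings only". Transfusion is on that list (listing 16.2.9.13). G-CSF has no handling of its own and would appear only with the concomitant medications.

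On missing values, SAP 6.1.7 states: "If one or more laboratory data are unavailable within the visit window, the LOCF approach will be used". Week 8 remission is one status within SD56 ± 5 days with no minimum duration. Time to remission runs to the first date on which the criteria are met. The SAP errata choose among several assessments by date and time only.

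**The concern.** Remission is meant to show that the laboratory features of MAS have normalised on emapalumab. A platelet count lifted by a platelet product, fibrinogen lifted by plasma or a fibrinogen product, or a WBC lifted by G-CSF does not show that. Read literally, the derivation still scores the component as met. LOCF can then place the same value at a later visit where nothing was measured.

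The study has one arm, so no control group shows how often support alone completes the laboratory criteria. No duration is required either, so a transient value can complete an event. At stake are the date of first remission, the occurrence of a first remission in some patients, and possibly the Week 8 status.

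**Working it through.** The plan states no figure that can be reproduced here: SAP 3.2 says that the sample size was not formally calculated, and no rate of transfusion or G-CSF use is given. The check is therefore a reading of the rules, followed by scale.

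**1. Is the gap there?** I compared the places that define remission or handle its inputs.

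- Protocol 7.4 and SAP 6.1.7: thresholds only.
- Protocol 12.3.5 and SAP 6.1.4: missing data, with nothing on support.
- SAP 8.1: efficacy analyses on two populations, with no sensitivity analysis for support.
- SAP errata, assessment selection: date and time only.
- SAP errata, MAS remission: stated to clarify assessment and window handling. The replacement wording is cut off in the text available to me, and nothing readable in it mentions support.
- Post-hoc analysis plan: adds a remission-assessment listing (16.2.6.2), with no mention of a support flag.

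No readable passage excludes, flags or tests supported values.

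**2. Who can be affected?** A false remission at a visit needs all of the following:

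- the clinical score, LDH, ALT/AST and ferritin criteria are met;
- at least one of WBC, platelets and fibrinogen would be below its threshold without support;
- recent support has lifted every such component above its threshold, and the rest of the three meet theirs unaided.

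If the patient later remits without support, the event is real but dated too early. If not, the first-remission event is false.

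**3. Which endpoint is more exposed?** Protocol Table 1 schedules the Investigator's MAS assessment at screening and then from SD6. Protocol 3.1 keeps patients in hospital until at least SD15. First remission can therefore be scored during the acute inpatient phase. Week 8 status is read from SD51 to SD61 (56 ± 5), which is 51 − 28 = 23 to 61 − 28 = 33 days after the planned end of dosing at SD28. Greater exposure for time to first remission is a reasonable inference; the documents do not state it.

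**4. Scale, using n of about 12 (SAP 3.2).** One patient is 1/12 = 8.3 points. With the minimum of 10 sJIA patients it would be 1/10 = 10.0 points. SAP 8.1 uses Clopper-Pearson intervals: lower limit = Beta quantile 0.025 with parameters (x, n − x + 1); upper limit = Beta quantile 0.975 with parameters (x + 1, n − x). The starting count of 10 and the one or two reclassifications are assumptions.

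| Remissions | Rate | 95% CI |
|---|---|---|
| 10/12 | 83.3% | 51.6–97.9 |
| 9/12 (one reclassified) | 75.0% | 42.8–94.5 |
| 8/12 (two reclassified) | 66.7% | 34.9–90.1 |

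If each of 12 patients had an independent chance q of a support-dependent remission, the chance of at least one is 1 − (1 − q)^12. That is 46% for q = 5%, 72% for q = 10% and 93% for q = 20%. These values of q are also assumptions.

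**The case against.** Several points on the other side stand.

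- Support cannot create a remission by itself, because four other criteria must hold at the same time.
- These components may seldom decide the outcome. Protocol 1.2.1 notes that sJIA patients often have raised white cells, platelets and fibrinogen, and that marked cytopenia and low fibrinogen come late in MAS. The fibrinogen entry criterion is at or below 360 mg/dL and is only one of four options, of which two are needed; the remission bar is 100 mg/dL. A patient can enter with fibrinogen already above that bar.
- LOCF carries low values forward as well as supported ones.
- All endpoints are exploratory and descriptive (SAP 4.1), so no error rate is at risk.
- Transfusions, concomitant drugs and remission assessments will all be listed by patient. With about 12 patients a reader could match them by hand.

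The last point is the strongest. But hand-matching leaves each reader to choose an interval and a product-to-component rule, and the reported proportion and Kaplan-Meier curve stay as they were.

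A reader might infer more than the documents support. They do not show that supported values were deliberately accepted; the gap is an omission. They do not show that the Week 8 rate is inflated, or by how much, since the reclassification counts above are hypothetical. They do not show that support data are ignored, since transfusions are recorded and listed.

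**Conclusion.** The concern holds in a limited form. As written, the rule can score a supported platelet, WBC or fibrinogen value as laboratory normalisation, and LOCF can extend it. Only a patient who would otherwise fail solely on one or more of those three components is affected. The likelier effect is on time to first remission, as an event dated too early or a false event. An effect on Week 8 remission is possible but less plausible.

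The size is unknown because no frequency of support is given; each affected patient would move a proportion by 8.3 points at n = 12. The conclusion assumes that the cut-off part of the errata adds no rule on support. This is an inexpensive improvement worth making. It is not a defect that invalidates the endpoint.

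**What to change.** Leave the primary remission definition and the permitted therapies as they are. Add to SAP 8.1 a sensitivity analysis of time to first remission and of Week 8 remission:

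- Map each product to its own component: platelet products to platelets, plasma or fibrinogen products to fibrinogen, G-CSF to WBC. Products that match none of the three, such as red cells, do not count.
- Have the sponsor pre-specify and justify a look-back interval. The gap between visits should not serve by default, because it runs from about 3 days early on to a week later and would act as a wash-out set by the schedule.
- Within that interval after the matching product, count the component as met only if the last unsupported value also met the threshold. Patients already above threshold before support are then not penalised.
- Do not carry supported values forward by LOCF.
- Flag support, by component, in listing 16.2.6.2.

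Before programming, confirm that the CRF holds product type and date, since the documents name only a Transfusion form, and check the rule against the full errata text. If the database is already locked, label the analysis post hoc, as the post-hoc plan does for its other outputs.

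The cost is a little programming and a sensitivity rate that may be slightly lower. If no remission depended on support, the analysis will show that.

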### 12.3.5 Missing Data

No imputations of missing data will be performed. However, the following rules will be applied to ensure that all patients can be included in the final analysis:

- patients who are withdrawn from the study prior to Week 8 because of safety concerns or poor efficacy will be classified as non-responders from the time of their withdrawal in all

analyses of response status, and their data will be censored at time of withdrawal in all time-to-event analyses. For continuous endpoints in such patients, all analyses for time points beyond the point of withdrawal will exclude missing data for these patients.

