## 6.1.5. Analysis Visit Windows

Statistical analyses will be based on scheduled visits as collected in the case report form (CRF) realigned on study days, which are defined based on the date of first emapalumab infusion (SD0) as follows:

Study Day = date of interest - date of first emapalumab infusion.

The following rules will be applied for MAS remission and glucocorticoid tapering.

- For the assessment of MAS remission and glucocorticoid tapering at Week 8, the SD56±5 days analysis period will be considered. Where several such observations occur in this time window, the one closest to SD56 will be selected. If there are 2 such observations that are equidistant from SD56, the observation that is after SD56 will be selected.
- For the assessment of time to MAS remission, see Section 6.1.7.

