For the analysis of systemic glucocorticoid dose tapering, conversion to prednisone-equivalent dose may be required, if different glucocorticoids have been administered. Furthermore, the glucocorticoid dose will be expressed as prednisone-equivalent mg/kg body weight/day.

AD-ST-33.04 Effective date: 30-Jun-2017

Version 2.0 | Date 29-Oct-2020 | AD-PR-109.01 Effective date: 26-Jun-2017

Page 21 of 51

Steps to calculate the prednisone equivalent dose (mg/kg/day):

- 1) Select systemic glucocorticoids where route is IV or oral from the 'Systemic glucocorticoids from SD-3 until SD15' form. Reported doses in the 'Systemic glucocorticoids from SD-3 unit SD15' form are daily doses and the number of doses per day is set to 1.
- 2) Select concomitant medications with ATC code H02B (Glucocorticoids) from the 'Concomitant medication' form with IV or oral route of administration. Calculate the frequency per day as follows (this list should not be seen as exhaustive):

Frequency	Description	Number of doses per day
OB, QD	Once a day	1
BID	Twice a day	2
TIB	Three times a day	3
QID	Four times a day	4
QW	Every week	1/7
2xW	Twice per week	2/7
3xW	Three times per week	3/7
NxW	N times per week	N/7
EVERY 2 WEEKS	Every 2 weeks	1/14
QM	Every month	1/30.4375
QAD	Every other day	0.5
Once	Single intake	1/(stop date – start date +1)
PRN	As needed	0
Other	Other	0
UNK	Unknown	0

AD-ST-33.04 Effective date: 30-Jun-2017

Version 2.0 | Date 29-Oct-2020 | AD-PR-109.01 Effective date: 26-Jun-2017

CI	Continuous infusion	0

Note: Administration of glucocorticoids with 'as needed', 'other', or 'unknown' frequency will not be included in the calculation of the equivalent dose.

- 3) If the dose unit is not mg, then the following conversion will be done: 1 g = 1000 mg, 1 mcg = 0.001 mg. IV and oral routes of administration are equivalent.
- 4) Select the weight in kg from the physical examination visit closest to the glucocorticoids administration date.
- 5) Calculate the equivalent dose of prednisone using the following formula:

Equivalent dose (mg/kg/day)= 
$$\frac{Conversion \ Factor * Dose(mg) * Number \ of \ doses \ per \ day}{Weight \ (kg)}$$

where the conversion factor is:

- 1 for prednisone
- 1.25 for methylprednisolone
- 1 for prednisolone
  - Glucocorticoids tapering = glucocorticoids permanently tapered
    - to the same (or lower) dose being administered before the occurrence of MAS (in patients already on treatment for sJIA/AOSD

or

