Version 2.0 | Date 29-Oct-2020 | AD-PR-109.01 Effective date: 26-Jun-2017

Page 24 of 51

date of first MAS remission – date of first emapalumab infusion + 1

Time to the first MAS remission will be calculated from the date of first emapalumab infusion until the date of first MAS remission. Patients who do not meet the criteria of MAS remission will be censored at the date of last contact.

The MAS remission evaluation is based on a combination of assessments, including Investigator assessment and laboratory findings. The latest date of assessments, within the visit window of  $\pm$  3 days around the planned day of the visit, will be used for the calculation of the time to MAS remission.

• Time to achievement of permanent glucocorticoids tapering:

date of glucocorticoids tapering – date of first emapalumab infusion + 1

Time to achievement of glucocorticoids tapering will be calculated from the date of first emapalumab infusion until the date in which the target level of glucocorticoid dose reduction is permanently achieved. Patients who do not meet the criteria of glucocorticoids tapering will be censored at the date of last contact.

• The total daily dose of anakinra, canakinumab, ciclosporin, etoposide, methotrexate, and tocilizumab will be calculated for each subject using the same unit of measurement provided in the concomitant medication log.

Total daily dose = dose \* Number of doses per day

Where the number of doses per day are derived using the same approach for the calculation of the equivalent dose of prednisone equivalent.

• Glucocorticoids tapering to  $\leq 1$  mg/kg/day of the equivalent dose of prednisone:

Achievement of permanent glucocorticoids tapering and last equivalent dose of prednisone is  $\leq 1$  mg/kg/day.

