## 8. Efficacy Analysis

## 8.1. Efficacy Analysis

The following binary efficacy endpoints will be described using counts, proportions, and exact Clopper-Person 95% CI:

- Patients achieving MAS remission by Week 8 after initiation of emapalumab treatment
- Patients for whom at any time during the study glucocorticoids can be tapered
- Patients who tapered steroids to ≤1 mg/kg/day of prednisone equivalent dose
- Patients withdrawn from the study due to lack of efficacy

The following time-to-event efficacy endpoints will be analyzed descriptively:

- Time to first MAS remission
- Time to achievement of permanent glucocorticoids tapering
- Survival time

Summaries will include for each observed time, the survival estimate, failure rate, number of events and the number of patients remaining, also called population at risk. The median, lower quartile and upper quartile estimates of time-to-event and their 95% CI will be tabulated in a separate table. A Kaplan–Meier graph will be presented for each time-to-event endpoint.

The efficacy analysis will be based on the All Treated Population. Efficacy analyses will be repeated for the EVAL Population.

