derivation of
equivalent dose of
prednisone or daily
dose of anakinra,
).
■ If Study day -180 ≤
medication start
date < Study day 0,
then medication
end date is set to
medication start
date.
• If medication start
$date \ge Study day 0,$
then medication
end date is set to
end of study date of

[figure not shown]
Version 2.0 | Date 22-Jul-2021 | AD-PR-109.02 Effective date: 17-Aug-2020 Page 11 of 18

		the corresponding patient.  • When "Ongoing" is ticked, then medication end date is set to end of study date of the corresponding patient unless medication start date > end of study date then set to medication start date of the corresponding patient.  -Medication start date is missing (and Medication end date is not missing)  • If medication end date < Study day -180, then this record will not be considered (i.e. no derivation of equivalent dose of prednisone or daily dose of anakinra,).  • If medication end date ≥ Study day -180, then the medication start date will be set to the medication end date.  Note: medication end date if available should have priority over
		the ongoing flag.
Section 6.1.8 - Data Adjustments/ Handling/ Conventions/ Handling < LLOQ, > ULOQ	No details regarding how the laboratory data below or above the limit of quantification will be handled.	Imputation rules to be applied to shift table when laboratory data below or above the limit of quantification. Laboratory listings will present data as collected.  / Imputation rules added: "Values
		below the lower limit of quantitation (i.e. < LLOQ) for individual values will be imputed to zeros when summarizing for

[figure not shown]
 Version 2.0
 Date 22-Jul-2021
 AD-PR-109.02
 Effective date: 17-Aug-2020
 Page 12 of 18

		descriptive statistics. Values above the upper limit of quantitation (i.e. > ULOQ) for individual values will be imputed to ULOQ values when summarizing for descriptive statistics."
Section 7.2 – Protocol Deviations / Correction	"Relevant protocol deviations categorized as major and minor will be tabulated in a summary table. Individual major and minor protocol deviations will be listed by patient."	Change in category terminology (applicable to the classification of deviations from a study conduct perspective) to align with references in regulations ICH E3 Q&A R1 and ICH GCP E6 R2.

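### A patient who dies while on a tapered steroid dose is scored as a tapering success, and one withdrawn for safety or lack of efficacy can be

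*SAP*

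**What the plan says.** **Definition.** SAP 6.1.7 reads "Glucocorticoids tapering = glucocorticoids permanently tapered", with two targets: the pre-MAS dose, or a cut of at least half from the dose at SD0. The event date for time to tapering is "the date in which the target level of glucocorticoid dose reduction is permanently achieved". No minimum duration, confirmatory observation or required follow-up is given. The added ≤1 mg/kg/day endpoint requires permanent tapering plus a last prednisone-equivalent dose at or below that level.

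**Endpoint and window.** SAP 8.1 lists the binary endpoint as "Patients for whom at any time during the study glucocorticoids can be tapered". SAP 6.1.5 adds "For the assessment of MAS remission and glucocorticoid tapering at Week 8, the SD56±5 days analysis period will be considered", but no tapering endpoint in 8.1 is tied to that window.

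**Missing doses.** SAP 6.1.7 says that "the assumption that dose has not been further tapered from the previous available observation will be made". Under the SAP errata to 6.1.8, for a record ticked as ongoing, "medication end date is set to end of study date of the corresponding patient unless" the record starts after that date.

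**Censoring.** SAP 6.1.7: "Patients who do not meet the criteria of glucocorticoids tapering will be censored at the date of last contact". Nothing is said about patients who meet the criteria and then die or leave.

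**Protocol rule.** Protocol 12.3.5 says "patients who are withdrawn from the study prior to Week 8 because of safety concerns or poor efficacy will be classified as non-responders", counted from withdrawal, in analyses of response status. In time-to-event analyses they are censored at withdrawal. Death is not mentioned. SAP 6.1.4 does not repeat the rule. SAP 11 does not list it as dropped and states that there are no further departures from the protocol's analyses.

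**The concern.** Permanence can only be judged while doses are being recorded. Death ends the record, and so in practice does withdrawal for worsening disease, since Protocol 6.5 then hands the patient to local standard of care. Protocol 6.1 expects a higher steroid dose to be re-introduced if disease worsens after tapering, so a dose increase is the sign on study that a taper has failed. A patient whose record stops before that increase is written down keeps a taper that was never tested.

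The truncation is therefore informative, and its bias runs one way: it raises the taper proportion and adds events to the time-to-taper curve. The study has no control arm in which the same bias would appear, and SAP 4.2 says a descriptive summary of efficacy was prepared for health authority meetings. Patients who leave for safety or lack of efficacy are not replaced (Protocol 12.5.1, SAP 6.1.4), so they stay in the denominator and their classification matters.

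**Working it through.** The plan states no expected taper rate or power, so there is no figure to reproduce. The check has two parts.

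**1. Which rule decides each case.** Take a patient who has reached target, has no recorded dose above target afterwards, and then leaves before Week 8.

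| Reason for leaving | Binary endpoints | Time to tapering |
|---|---|---|
| Death | Neither document has a rule. SAP 6.1.7 as written gives success. | The event dated before death stands. |
| Safety or lack of efficacy | SAP is silent. Protocol 12.3.5 gives non-responder from withdrawal if tapering is a response status; otherwise success. | Protocol 12.3.5 censors at withdrawal, so the earlier event stands. The SAP gives the same result. |

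Two ambiguities keep the lower left cell open. Protocol 12.3.5 does not say whether tapering is a response status. A classification that starts at withdrawal also does not clearly undo a success credited earlier under an any-time definition.

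**2. Size.** Inputs: n = 12 (Protocol 12.1, SAP 3.2) and exact Clopper-Pearson 95% intervals (SAP 8.1). The success counts are assumptions.

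Lower limit = Beta quantile(0.025; x, n − x + 1). Upper limit = Beta quantile(0.975; x + 1, n − x). Each reclassified patient moves the rate by 1/12 = 8.3 percentage points.

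- 9/12 = 75.0% (42.8–94.5), with one such patient counted as a success
- 8/12 = 66.7% (34.9–90.1), with that patient counted as non-tapered
- 7/12 = 58.3% (27.7–84.8), with two patients reclassified

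For plausibility, P(at least one death among 12) = 1 − (1 − p)^12. For p = 5%, 10%, 20% and 30% this is 0.46, 0.72, 0.93 and 0.99. The 20–30% end is the background mortality cited in Protocol 1.2.1; the lower values are assumptions. Death after reaching target is a subset of these events, so the figures are upper bounds for the death route.

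**Kaplan-Meier estimate.** Suppose nine patients have events and three are followed event-free. The final estimate is 1 − 3/12 = 75.0%. If one of the nine becomes a non-event and stays in the risk set to the end, it is 1 − 4/12 = 66.7%. If that patient is instead censored on leaving, the result depends on timing. In the extreme case of leaving before the other eight events, it is 1 − 3/11 = 72.7%. The sensitivity analysis must therefore say where these patients leave the risk set.

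**The case against.** The strongest reply is that the protocol already protects the withdrawal case. SAP 11 does not remove the rule in Protocol 12.3.5, and silence in SAP 6.1.4 is not contradiction. This stands. A reader might infer that the SAP contradicts the protocol, or that a patient withdrawn for lack of efficacy simply counts as a success. The documents support only that such a patient can be so counted, because the rule is not restated and its reach is unclear. The reply does not help with death, which Protocol 12.3.5 does not address.

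A second reply is that the missing-dose rule prevents credit for undocumented reductions and extrapolates nothing past the patient's own end of study. This is also right: no dose is carried to SD56. The difficulty is that permanence is judged over whatever record exists, however short.

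Third, a worsening patient would often have a recorded dose increase, which would defeat permanence, and the withdrawal visit (Protocol 8.9) includes concomitant medication. This narrows the group affected but does not empty it.

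Fourth, a reader might infer that every patient should have observed doses at target through SD56. The documents do not support this. The protocol endpoint is tapering at any time, and such a requirement would turn it into a Week 8 endpoint. It would also fail patients who leave for administrative reasons.

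Finally, all variables are exploratory and without hierarchy (SAP 4.1). Survival and lack-of-efficacy withdrawals are reported separately (SAP 8.1), and a planned listing shows remission, tapering and mortality together. This limits the harm but does not correct the tapering rate itself.

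**Conclusion.** The point holds in a limited form. For death after the target is reached, the SAP as written scores a success and no rule in either document says otherwise. For withdrawal before Week 8 on safety or efficacy grounds, a success is possible because the protocol's rule is left out of the SAP undeclared and is unclear for an any-time endpoint. For time to tapering, SAP and protocol agree in leaving the earlier event in place, so changing that would go beyond the protocol; this is why a sensitivity analysis is the right form.

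The bias is upward by 8.3 points per affected patient at n = 12. The number affected is unknown, and the documents give no rate for reaching target and then dying or being withdrawn. Given descriptive endpoints and separate reporting of failures, the impact is modest but worth correcting.

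**What to change.** In SAP 6.1.4 and 6.1.7, state that patients who die, or who are withdrawn before Week 8 for safety or lack of efficacy, count as non-tapered in both binary tapering endpoints (any-time tapering and ≤1 mg/kg/day). This applies Protocol 12.3.5 and extends it to death. List the extension in SAP 11.

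For time to tapering, keep the planned analysis and add a sensitivity analysis in which these patients are not events. Say how they are held; keeping them in the risk set to the end of planned follow-up makes the final estimate agree with the binary proportion when no one else is censored early.

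Do not require observed doses through SD56 for all patients.

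The cost is a few sentences and one extra table. The downside is a possibly lower reported taper rate. The errata already revise the steroid-dose derivations before database lock, so the change fits there.
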